6.3. Reversal medication

There is currently no specific antidote for MAA868. FXI concentrates (not marketed in the US) are unlikely to be effective as the excess in free MAA868 concentrations in the circulation is expected to quickly neutralize the exogenous FXI.

Recombinant FVIIa can bypass the hypocoagulopathy and restore hemostasis in patients with severe FXI deficiency. Administration of intermediate to high doses of rFVIIa (40 to 90 µg/kg) resulted in supra-physiological levels of FVII and thromboembolic complications in patients with severe FXI deficiency (Riddell et al 2011). Low doses of rFVIIa are associated with lower prothrombotic risk. Riddell et al reported their experience in 4 patients with severe FXI deficiency undergoing surgery (Riddell et al 2011); patients were administered rFVIIa 30 µg/kg and tranexamic acid 1 g i.v. at induction of anesthesia. Subsequent bolus doses of rFVIIa 15–30 µg/kg were administered at 2 to 4 hourly intervals as guided by rotational thromboelastometry for 24 48 hours and tranexamic acid 1 g every 6 hourly for 5 days. Low doses of rFVIIa and tranexamic acid were safe and effective in restoring hemostasis in severe FXI deficiency in this study. In another study comprising 4 patients with severe FXI deficiency with inhibitor who experienced 5 surgeries (Livnat et al 2009), 1 g of tranexamic acid was given 2 hours before surgery, immediately prior to the interventions then every 6 hour for at least 7 days; moreover, rFVIIa was administered at doses ranging from 15 to 30 µg/kg at the completion of surgery. This protocol secured normal hemostasis in patients with severe FXI deficiency with inhibitor.

Based on the above, rFVIIa can be recommended as a preferred therapeutic option to restore hemostasis in subjects with active, non-accessible bleeding site and in subjects requiring immediate reversal of the MAA868 PD effects prior to an urgent surgery. Please see the Investigator's Brochure - Summary of the data and guidance for the investigator for a more complete discussion.

7. STUDY ASSESSMENTS AND PROCEDURES

7.1. Assessment schedule

Subjects should be seen for all visits/assessments as outlined in the assessment schedule ([Table 9](#)).

Missed or rescheduled visits should not lead to automatic discontinuation. Subjects who prematurely discontinue the study for any reason should be scheduled for a visit as soon as possible, at which time all of the assessments listed for the study treatment discontinuation (TD) visit will be performed.

7.2. Informed consent procedures

Eligible subjects may only be included in the study after providing written (witnessed, where required by law or regulation), IRB-approved informed consent.

The Sponsor, or Sponsor designee, will provide to investigators a proposed informed consent form that complies with the ICH E6 Good Clinical Practice (GCP) guideline and regulatory requirements and is considered appropriate for this study. The informed consent form will also include a section related to optional future research which will require a separate consent checkbox if the subject agrees to future research. Any changes to the proposed consent form suggested by the Investigator must be agreed to by the Sponsor before submission to the IRB.

Information about common side effects already known about the investigational drug can be found in the IB. This information will be included in the subject informed consent and should be discussed with the subject during the study as needed. Any new information regarding the safety profile of the investigational drug that is identified between IB updates will be communicated as appropriate, for example, via an Investigator Notification or an Aggregate Safety Finding. New information might require an update to the informed consent and then must be discussed with the subject.

Ensure subjects are informed of the contraception requirements outlined in the [Section 4.2](#) (Exclusion criteria).

A copy of the approved version of all consent forms must be provided to the Covance monitor after IRB approval.

7.3 Subject screening

In general, it is permissible to re-screen a subject if s/he fails the initial Screening or falls out of the screening window timelines; however, each case must be discussed and agreed with the Sponsor Medical Monitor on a case-by-case basis. A new screening number will be assigned to a subject who is re-screened, thus no screening number will be used twice.

Reasons for screen failure will be documented in the site log.

7.4 Subject demographics/other baseline characteristics

Subject demographic and baseline characteristic data will be collected on all subjects. Relevant medical history/current medical conditions data will also be collected until signature of informed consent.

Investigators have the discretion to record abnormal test findings on the medical history CRF, if in their judgment, the test abnormality occurred prior to the informed consent signature.

Hepatitis screen, HIV screen

All subjects will be screened for HIV, Hepatitis B and C.

Alcohol test and drug screening

All subjects will be screened for alcohol and substances of abuse.

7.5 Efficacy Assessments

The PD samples will be collected at the timepoints defined in the Assessment schedule (Table 9). Follow instructions outlined in the Central Laboratory Manual regarding sample collection, numbering, processing and shipment.

In order to better define the PD profile, the timing of the sample collection may be altered based on emergent data. The number of samples/blood draws and total blood volume collected will not exceed those stated in the Laboratory Manual.

PD samples will be obtained and evaluated in all subjects at all dose levels.

7.5.1 Free FXI

Free FXI concentrations (FXI that is not bound to MAA868) will be measured in plasma. A detailed description of the assay methods will be included in the Bioanalytical Data Report.

7.5.2 aPTT

aPTT, calibrated for FXI deficiency, and aPTT using a standard laboratory protocol and/or point of care device will be measured at all timepoints indicated in the Assessment schedule (Table 9).

aPTT will be determined in plasma. The detailed method descriptions of the assay will be included in the Bioanalytical Data Report.

7.5.3 Total FXI

Total FXI concentrations (FXI that is either bound to MAA868 or free) will be measured in plasma. A detailed description of the assay methods will be included in the Bioanalytical Data Report.

7.5.4 FXI coagulation activity (FXI:C)

FXI:C will be measured in plasma. A detailed description of the assay methods will be included in the Bioanalytical Data Report.

7.6 Safety Assessments

Safety assessments are specified below; assessments will be collected as specified in the Assessment Schedule (Table 9).

Bleeding

All suspected bleeding events will be documented by the Investigator in the appropriate CRF. All documentation regarding suspected bleeding events will be forwarded for adjudication. The central

independent adjudication committee (CIAC) will classify the bleeding events as major bleeding, CRNM bleeding, nuisance bleeding, or no bleeding. For definition of major bleeding the criteria of the International Society of Thrombosis and Haemostasis (ISTH) for non-surgical patients ([Schulman et al 2005](#)) is referred to. Further definitions can be found in the CIAC charter.

The members of the CIAC will be blinded to treatment assignment. Further details and procedures surrounding adjudication of bleeding events are in the CIAC charter.

The population is those who have received at least one dose of the study drug.

Major cardiovascular, cerebrovascular, and venous thromboembolic events

All suspected major cardiovascular, cerebrovascular, and VTE events will be documented by the Investigator in the appropriate CRF including any diagnostic imaging that was used to confirm the event. For instance, any suspected episodes of DVT (i.e., swelling, localized pain, redness, heat, localized warmth) must be documented by compression ultrasound (CUS) or venography.

Any suspected episodes of PE (i.e., shortness of breath, chest pain, coughing, tachycardia, hemoptysis, hemodynamic compromise, unexplained death) must be documented by ventilation/perfusion lung scintigraphy, spiral computed tomography (sCT), or pulmonary angiography.

All major cardiovascular, cerebrovascular, systemic arterial, and venous thromboembolic events (VTEs) including deaths for which a major cardiovascular, cerebrovascular, or VTE event could not be ruled out will be adjudicated by experienced medical personnel that is blinded to treatment assignment.

The adjudicated outcome will be the basis for any interim and final safety evaluations.

7.6.1 Adverse Events

An AE is any untoward medical occurrence [i.e., any unfavorable and unintended sign (including abnormal laboratory findings), symptom or disease] in a subject or clinical investigation subject after providing written informed consent for participation in the study until the EoS visit. Therefore, an AE may or may not be temporally or causally associated with the use of a medicinal (investigational) product.

In addition, all reports of intentional misuse and abuse of the study treatment are also considered an AE irrespective if a clinical event has occurred. See [Section 7.6.2](#) for an overview of the reporting requirements.

The occurrence of AEs must be sought by non-directive questioning of the subject at each visit during the study. AEs also may be detected when they are volunteered by the subject during or between visits or through physical examination finding, laboratory test finding, or other assessments.

Abnormal laboratory values or test results constitute AEs only if they fulfill at least one of the following criteria:

- they induce clinical signs or symptoms,
- they are considered clinically significant,
- they require therapy.

Clinically significant abnormal laboratory values or test results should be identified through a review of values outside of normal ranges/clinically notable ranges, significant changes from baseline or the previous visit, or values which are considered to be non-typical in healthy subjects. Investigators have the responsibility for managing the safety of individual subject and identifying AEs. Alert ranges for liver and kidney related events are included in [Appendix 1](#) and [Appendix 2](#), respectively. Additional clinically notable laboratory values are included in [Appendix 3](#).

AEs must be recorded on the AE CRF under the signs, symptoms or diagnosis associated with them, and accompanied by the following information:

1. Severity grade

- mild: usually transient in nature and generally not interfering with normal activities
- moderate: sufficiently discomforting to interfere with normal activities
- severe: prevents normal activities

2. Relationship to the study treatment

- Related
- Possibly related
- Not related

3. Duration (start and end dates) or if the event is ongoing an outcome of not recovered/not resolved must be reported.

4. Whether it constitutes a SAE (see [Section 7.6.2](#) for definition of SAE) and which seriousness criteria have been met

5. Action taken regarding investigational treatment.

All AEs must be treated appropriately. Treatment may include one or more of the following:

- no action taken (e.g. further observation only)
- concomitant medication or non-drug therapy given
- hospitalization/prolonged hospitalization (see [Section 7.6.2](#) for definition of SAE)

6. Outcome (not recovered/not resolved; recovered/resolved; recovering/resolving, recovered/resolved with sequelae; fatal; or unknown).

Information about common side effects already known about the investigational drug can be found in the IB. Once an AE is detected, it must be followed until its resolution or until it is judged to be permanent, and assessment should be made at each visit (or more frequently, if necessary) of any changes in severity, the suspected relationship to the investigational drug, the interventions required to treat it, and the outcome.

The Investigator must also instruct each subject to report any new AE (beyond the protocol observation period) that the subject, or the subject's personal physician, believes might reasonably be related to study treatment. This information must be recorded in the Investigator's source documents; however, if the AE meets the criteria of an SAE, it must be reported to Covance.

7.6.2 Reporting Serious Adverse Events

Definition of SAE

An SAE is defined as any AE [appearance of (or worsening of any pre-existing) undesirable sign(s), symptom(s) or medical conditions(s)] which meets any one of the following criteria:

- is fatal or life-threatening
- results in persistent or significant disability/incapacity
- constitutes a congenital anomaly/birth defect
- requires inpatient hospitalization or prolongation of existing hospitalization, unless hospitalization is for:
 - elective or pre-planned treatment for a pre-existing condition and has not worsened since the start of study drug
 - treatment on an emergency outpatient basis for an event not fulfilling any of the definitions of a SAE given above and not resulting in hospital admission
 - social reasons and respite care in the absence of any deterioration in the subject's general condition
 - is medically significant, e.g. defined as an event that jeopardizes the subject or may require medical or surgical intervention

All malignant neoplasms will be assessed as serious under “medically significant” if other seriousness criteria are not met.

Life-threatening in the context of a SAE refers to a reaction in which the subject was at risk of death at the time of the reaction; it does not refer to a reaction that hypothetically might have caused death if it were more severe (see Annex IV, ICH-E2D Guideline).

Medical and scientific judgment should be exercised in deciding whether other situations should be considered serious reactions, such as important medical events that might not be immediately life threatening or result in death or hospitalization but might jeopardize the subject or might require intervention to prevent one of the other outcomes listed above. Examples of such events are intensive treatment in an emergency room or at home for allergic bronchospasm, blood dyscrasias or convulsions that do not result in hospitalization or development of dependency or abuse (see Annex IV, ICH-E2D Guideline).

Any suspected transmission via a medicinal product of an infectious agent is also considered a serious adverse reaction.

All AEs (serious and non-serious) are captured on the CRF; SAEs also require individual reporting to Covance Drug Safety & Epidemiology (DS&E).

SAE Reporting

To ensure subject safety, every SAE, regardless of causality, occurring after the subject has provided informed consent and until 30 days after the last planned study assessment, must be reported to Covance within 24 hours of learning of its occurrence as described below. Any SAEs

experienced after this period should only be reported to Covance if the Investigator suspects a causal relationship to study treatment.

Note: SAEs reported by subjects deemed to be screen failures must be reported to Covance as outlined here with appropriate information also captured in the CRFs.

All follow-up information for the SAE including information on complications, progression of the initial SAE and recurrent episodes must be reported as follow-up to the original episode within 24 hours of the Investigator receiving the follow-up information. An SAE occurring at a different time interval or otherwise considered completely unrelated to a previously reported one must be reported separately as a new event.

Follow-up information provided must describe whether the event has resolved or continues, if and how it was treated, whether the blind was broken or not (if applicable) and whether the subject continued or withdrew from study participation. Each re-occurrence, complication, or progression of the original event must be reported as a follow-up to that event regardless of when it occurs.

If the SAE is not previously documented in the IB (new occurrence) and is thought to be related to the study treatment a Covance DS&E associate may urgently require further information from the Investigator for Health Authority reporting. Covance may need to issue an Investigator Notification (IN) to inform all investigators involved in any study with the same study treatment that this SAE has been reported. Suspected Unexpected Serious Adverse Reactions (SUSARs) will be collected and reported to the competent authorities and relevant ethics committees in accordance with EU Guidance 2011/C 172/01 or as per national regulatory requirements in participating countries.

Follow the detailed instructions outlined in the Safety Management Plan regarding the submission process for reporting SAEs to Covance. Note: SAEs must be reported to Covance within 24 hours of the Investigator learning of its occurrence/receiving follow-up information.

7.7 Liver safety monitoring

To ensure subject safety and enhance reliability in determining the hepatotoxic potential of an investigational drug, a standardized process for identification, monitoring and evaluation of liver events must be followed.

Please refer to [Appendix 1](#) for complete definitions of liver events.

Follow-up of liver events

Every liver event defined in [Appendix 1](#) should be followed up by the Investigator or designated personnel at the trial site, as summarized below. Additional details on actions required in case of liver events are outlined in [Table 4](#) of Appendix 1.

- Repeating liver chemistry tests (ALT, AST, total bilirubin (TBL), PT/INR, ALP and γ GT) to confirm elevation as soon as possible

These liver chemistry repeats should always be performed using the central laboratory, with the results provided via the standard electronic transfer. If results are needed quickly then the repeats can also be performed at a local laboratory to monitor the safety of the subject. If a liver event is subsequently reported, any local liver chemistry tests previously

conducted that are associated with this event should be available to Covance and the Sponsor.

- If the initial elevation is confirmed, close observation of the subject will be initiated, including consideration of treatment interruption if deemed appropriate.
- Discontinuation of the investigational drug (refer to [Section 4.3](#) (Discontinuation of study treatment)), if appropriate
- Hospitalization of the subject if appropriate
- Causality assessment of the liver event
- Thorough follow-up of the liver event should include
 - Repeating liver chemistry tests two or three times weekly. Testing should include ALT, AST, ALP, PT/INR, and γ GT. If total bilirubin is elevated $> 2 \times$ ULN, fractionation into direct and indirect bilirubin is required. To rule out muscular origin of transaminase elevations, CPK should be measured along with liver chemistry tests. Frequency of retesting can decrease to once a week or less if abnormalities stabilize or the study drug has been discontinued and the subject is asymptomatic. Retesting should be continued up to resolution.
 - Obtaining a more detailed history of symptoms and prior or concurrent diseases.
 - Obtaining a history of concomitant drug use (including non-prescription medications and herbal and dietary supplement preparations), alcohol use, recreational drug use, and special diets.
 - Exclusion of underlying liver disease, as specified in [Table 6](#).
 - Imaging such as abdominal US, CT or MRI, as appropriate
 - Obtaining a history of exposure to environmental chemical agents.
 - Considering gastroenterology or hepatology consultations.

All follow up information, and the procedures performed must be recorded as appropriate in the CRF.

7.8 Renal safety monitoring

Renal laboratory alerts and renal events must be followed up by the Investigator or designated personnel at the trial site. Recommended follow-up assessments are listed in [Appendix 2](#).

7.9 Pregnancy

All female study participants, regardless of the requirement to be of non-child-bearing potential to be enrolled into this study, will have pregnancy testing. See the Assessment Schedule ([Table 9](#)), for timing of the protocol required pregnancy testing; additional pregnancy testing may be performed to meet local requirements*. Subjects will not receive study medication in case of a positive urine or serum pregnancy test.

*If additional pregnancy testing is needed per local requirements, those additional results will be kept as source documentation only.

Pregnancy reporting

Reproductive toxicity and teratogenicity data are not available for this antibody at this time, therefore no guidelines on therapeutic recommendations in case of pregnancy are available. This study enrolls women who are considered to be of non-child-bearing potential, thus pregnancy is not an expected outcome for any female study participant. However, in the case that a pregnancy in a female study participant should occur please follow the below reporting guidelines. The follow-up for this subject and for the fetus is at the discretion of the Investigator.

To ensure subject safety, each pregnancy occurring after signing the informed consent must be reported to Covance within 24 hours of learning of its occurrence. The pregnancy should be followed up to determine outcome, including spontaneous or voluntary termination, details of the birth, and the presence or absence of any birth defects, congenital abnormalities, or maternal and/or newborn complications.

Pregnancy must be recorded on the Pharmacovigilance Pregnancy Form and reported by the Investigator to the local Covance DSS department. Pregnancy follow-up should be recorded on the same form and should include an assessment of the possible relationship to the study treatment.

Any SAE experienced during the pregnancy and unrelated to the pregnancy must be reported on a SAE form.

Pregnancy outcomes should be collected for the female partners of any males who took study treatment in this study. Consent to report information regarding these pregnancy outcomes should be obtained from the mother.

All assessments that are considered as a risk during pregnancy must not be performed. The subject may continue all other protocol assessments.

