3. INVESTIGATION PLAN

3.1. Overall Study Design and Plan Description

This is a phase 2a, randomized, subject- and investigator-blinded, placebo-controlled, multiple ascending dose-ranging study to assess the PK/PD, safety, tolerability, and immunogenicity of MAA868 in patients with AF or flutter.

Patients will be enrolled in at least 2 and up to 3 cohorts of approximately 16 patients each for a total of up to 48 subjects (Figure 1A). Patients in cohort 1 will be randomized 3:1 to receive a 120 mg dose of MAA868 or placebo, respectively on Day 1 with two subsequent monthly injections. After approximately 10 of the patients in cohort 1 have been randomized, a safety review of emerging safety and PK data from cohort 1 will take place. Cohort 2 may be initiated after it is confirmed by the Sponsor’s Medical Monitor and the Covance Lead Project Physician that the cohort 1 dose was safe and well tolerated after at least half of the patients in cohort 1 have been randomized. Likewise, after approximately 10 of the patients in cohort 2 have received their second dose and have been followed for at least an additional 14 days, interim safety, tolerability, and other analyses will be evaluated by the Sponsor. Based on emerging data, the Sponsor may elect to:

[figure not shown]
- Enroll cohort 3 to evaluate a higher, lower, or a previously studied dose of MAA868
- Terminate the study

The study is comprised of 3 periods:

- (1) Screening period of up to 28 days
- (2) Treatment period with MAA868 administered s.c. monthly (or matching placebo) (randomized 3:1) for 90 days
- (3) Follow-up period up to end of study (Day 170).

Following the screening period of up to 28 days, all patients that meet the study eligibility criteria (Section 4.1 and Section 4.2) will have baseline efficacy and safety assessments performed on Day 1 and then randomized to active or placebo (Figure 1B).

Figure 1: Overall study design

The first dose of study drug will be administered at the study center on Day 1. The second and third doses of study drug will also be administered at the study center to patients on the Day 31 visit and Day 61 visit, respectively.

During the treatment period, patients will return to the study center on Day 11, Day 31, Day 41, Day 61, Day 71, and Day 91 for safety assessments such as vital signs, AE assessments, laboratory tests, PK, PD, thrombogenesis biomarkers, and other study assessments according to the assessment schedule shown in [Table 9](#).

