4.2. Exclusion Criteria

1. Use of other investigational drugs at the time of enrollment, or within 5 half-lives of enrollment, or until the expected PD effect has returned to baseline, whichever is longer; or longer if required by local regulations.
2. History of stroke, transient ischemic attack or systemic embolism
3. History of major bleeding during treatment with an anticoagulant or antiplatelet therapy. (Patients who have had major bleeding on anticoagulants or antiplatelet therapy more than a year ago can be enrolled only if the bleeding was due to a reversible cause, e.g. gastro-duodenal ulcer that was successfully treated.)
4. History of traumatic or non-traumatic intracranial, intraspinal or intraocular bleeding
5. Known bleeding diathesis or any known active bleeding site at screening or baseline
6. Family history of bleeding disorder
7. Known active GI lesions predisposing to bleeding events
8. Myocardial infarction, unstable angina pectoris or coronary artery bypass graft (CABG) surgery within 12 months prior to the Screening period
9. Known clinically significant valvular heart disease including moderate or severe mitral stenosis (valve area < 1.5 cm²).
10. Patients with a prosthetic heart valve
11. Uncontrolled hypertension defined as SBP/DBP $\geq 160/100$ mmHg at the Screening visit
12. Patients with NYHA Class III- IV heart failure
13. Currently being treated with anticoagulant therapy or have been on anticoagulants in the previous 12 months. Potential patients who have been on anticoagulation more than 12 months ago requires discussion with the sponsor before enrolling.
14. Treatment with antiplatelet therapy such as either a P2Y12 inhibitor or aspirin. (Low dose aspirin ≤ 100 mg/d) is allowed.)
15. Severe renal impairment as defined as an estimated glomerular filtration rate ≤ 45 mL/min/1.73m² by the MDRD equation at the Screening Visit

16. Positive test for human immunodeficiency virus (HIV), positive hepatitis B (hepatitis B surface antigen [HBsAg]) or hepatitis C (anti-hepatitis C antibody [Anti-HCV]) at Screening
17. Significant illness, per Investigator judgement, which has not resolved within four (4) weeks prior to dosing
18. Women of child-bearing potential, defined as all women physiologically capable of becoming pregnant, unless they are using highly effective methods of contraception during their time in the study. Highly effective contraception methods include:

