5.6. Permitted dose adjustments and interruptions of study treatment

Dosing interruptions are permitted in the case of logistical reasons not related to study therapy, e.g., an unrelated event such as a COVID-19-related travel restriction or any other restriction or safety concern with the subject traveling to the study site. The reason for interruption should be documented in the patient's study record.

Once the restriction(s) leading to study drug interruption have been lifted and the Sponsor and Investigator agree that it is safe for the subject to resume study participation, the subject may be resumed on study therapy on a case-by-case basis upon discussion with the Sponsor. Subjects who received only 1 dose of study drug before interruption may either resume study drug with the second dose or may restart with the first dose of study drug if a sufficient amount of time has elapsed such that the expected PD effect has returned to baseline.

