6.2. Study restrictions

Pregnancy and contraception

Women of child-bearing potential are not permitted to participate in this study, unless they agree to use highly effective methods of contraception during their time in the study.

During their time in the study, sexually active male subjects must agree to use highly effective methods of contraception and should not father a child or donate sperm in this period.

Prohibited treatment

Use of the following medications is not allowed during the course of the study from screening (Visit 1) through the EoS. Patients who are receiving such medication(s) will be excluded, or if ethically and clinically justified, the medication(s) should be gradually withdrawn at least seven days before the baseline visit:

- Use of chronic antiplatelet agents such as clopidogrel or ticagrelor is prohibited; however, use of low-dose aspirin (≤ 100 mg per day) is permitted.
- Use of chronic systemic anticoagulants such as warfarin, low molecular weight heparin or heparinoids, or direct oral anticoagulants such as apixaban or dabigatran. Patients may be started on chronic anticoagulation during the Washout/Follow-up period once their aPTT has returned to baseline, at the Investigator's discretion.
- Use of any therapeutic monoclonal antibody regardless of the indication during the study.

Dietary restrictions

- No alcohol for 48 hours before each clinic visit (from Screening through the EoS visit). During the study, alcohol consumption will be restricted to no more than 2 drinks/day for males and 1 drink/day for females.
- Patients should not make significant alterations in their diet (e.g., going on weight loss diet) while in the study.
- During the study, caffeinated beverages will be restricted to no more than 3 cups/day.

Other restrictions

No strenuous physical exercise or activities which have an increased risk of injury or falling should be undertaken until after the EoS visit.

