12.4. Appendix 4 - Schedule of Assessments

Table 9: Schedule of Assessments

Period	Screening	Treatment							Washout / Follow-up			
Visit	1	2	3	4	5	6	7	8	9	10	TD	EoS
Day	-28 to -3	1 (predose)	11	31 (predose)	41	61 (predose)	71	91	101	121	-	170
Window			±2	±2	±3	±2	±3	±2	±3	±3		±10
Informed consent	X											
Medical history	X											
Drug & alcohol screen	X											
I/E criteria	X	X										
Physical Exam	X	X	X	X		X		X		X	X	X
Height	X											
Weight	X	X										X
Vital signs	X	X	X	X	X	X	X	X	X	X	X	X
12-lead ECG	X	X						X				X
HIV, Hepatitis B, Hepatitis C	X											
aPTT, Free and total FXI	X	X	X	X	X	X	X	X	X	X	X	X
aPTT (corrected for FXI), FXI:C		X				X		X				X
PK assessment: total MAA868		X	X	X	X	X	X	X	X	X		X
Antidrug antibodies (ADA)		X		X		X	X	X		X		X
Exploratory biomarker collection	X	X		X		X		X		X		
Complete safety Labs	X	X	X	X	X	X		X		X	X	X
Pregnancy test	Serum	Urine			Urine			Urine			Urine	Urine
Urine	X	X	X	X	X	X		X		X	X	X
Fecal occult blood test	X	X										
AE collection						X						
Concomitant meds						X						
Local assessment of CV and cerebrovascular events							X					
Local assessment of bleeding events							X					
Dispense Study Medications		X		X		X						
Drug Accountability		X		X		X		X				
MAA868		X		X		X						
Placebo		X		X		X						

Period	Screening	Treatment							Washout / Follow-up			
Visit	1	2	3	4	5	6	7	8	9	10	TD	EoS
Day	-28 to -3	1 (predose)	11	31 (predose)	41	61 (predose)	71	91	101	121	-	170
Window			±2	±2	±3	±2	±3	±2	±3	±3		±10
Injection site inspection (post-dose)		X	X	X	X	X	X					
Study disposition								X			X	X

TD = Study treatment discontinuation; EoS = End of Study; FXI:C = Factor XI coagulation activity

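### No pregnancy test is scheduled at the Day 31 or Day 61 dosing visits, so the withholding rule relies on a required result 30 days old at dose 2 and 20 days old at dose 3

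*Protocol*

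**What the plan says.** The rule in Protocol section 7.9 is "Subjects will not receive study medication in case of a positive urine or serum pregnancy test". The section covers all female participants and sends the reader to Table 9 for the timing. Beyond that, it says only that "additional pregnancy testing may be performed to meet local requirements".

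In Table 9 (Appendix 4, section 12.4) the row "Pregnancy test" shows serum at Screening and urine at Day 1 predose, Day 41, Day 91, the treatment discontinuation visit and end of study. The Day 31 and Day 61 cells are blank. Table 9 in the initial protocol and in Amendment 1 has the same row.

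Section 3.1 places dose 1 on Day 1 and continues: "The second and third doses of study drug will also be administered at the study center to patients on the Day 31 visit", with the third dose on Day 61.

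On who may enrol, section 4.2 no. 18 excludes women of child-bearing potential "unless they are using highly effective methods of contraception during their time in the study", and section 6.2 repeats the exception: "unless they agree to use highly effective methods of contraception during their time in the study". Section 7.9 itself describes the enrolled women as not of child-bearing potential. It also says that no reproductive toxicity or teratogenicity data exist for this antibody.

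Section 5.6 allows dosing to restart after an interruption once "the Sponsor and Investigator agree that it is safe for the subject to resume study participation". It adds: "Subjects who received only 1 dose of study drug before interruption may either resume study drug with the second dose", or start again from dose 1 if the drug effect has worn off. It does not mention a pregnancy test.

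**The concern.** A rule that withholds drug after a positive test can act only if a result is available when the dose is due. Between dose 1 and dose 2 the protocol requires no test. The Day 1 result was already used to release dose 1, so it cannot stop dose 2. The Day 41 test falls ten days after dose 2 and can affect only dose 3. The Day 91 test comes after the last dose.

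A site that follows the plan exactly could therefore give dose 2 to a woman who conceived after Day 1. She already carries dose 1, so a Day 31 test would not prevent exposure. It would let the site avoid a further dose of a long-acting antibody whose reproductive effects are unknown and which, according to section 6.3, has no specific antidote. After an interruption under section 5.6, the last required result could be older still.

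This is a gap in the schedule and not a contradiction, because section 7.9 does not ask for a negative result before each dose.

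**Working it through.** **Reading the row.** The Table 9 visit, day and pregnancy-test rows each have a label and 12 cells. The last two urine entries fall on the treatment discontinuation and end-of-study columns, so the row has not shifted in extraction.

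| Dose | Day | Newest required test | Age, nominal | Age with visit windows |
|---|---|---|---|---|
| 1 | 1 | Day 1 predose | 0 days | 0 days |
| 2 | 31 (±2) | Day 1 | 31 − 1 = 30 days | 29 − 1 = 28 to 33 − 1 = 32 days |
| 3 | 61 (±2) | Day 41 (±3) | 61 − 41 = 20 days | 59 − 44 = 15 to 63 − 38 = 25 days |

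**What withholding dose 2 would save.** The plan gives no figure to reproduce. Section 1.1 reports, from the first-in-human study, a mean terminal half-life of 20 to 28 days and a median time to peak of Day 7 to 21. I assume linear one-compartment kinetics with first-order absorption and equal doses, and treat the time to peak as days after dosing.

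*Elimination only.* The fraction of dose 1 left 30 days later is 0.5^(30/t½):
- 0.5^(30/20) = 0.354
- 0.5^(30/28) = 0.476

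*With absorption.* Set ke = ln 2 / t½ and solve ka from Tmax = ln(ka/ke)/(ka − ke). The fraction of the dose 1 AUC still to come after 30 days is

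f = (ka·e^(−30ke) − ke·e^(−30ka)) / (ka − ke).

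After Day 31, exposure is proportional to f if dose 2 is withheld and to 1 + f if it is given. The ratio is (1 + f)/f.

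| t½ (days) | Tmax (days) | ka (per day) | f | (1 + f)/f |
|---|---|---|---|---|
| 20 | 7 | 0.375 | 0.390 | 3.57 |
| 20 | 21 | 0.063 | 0.600 | 2.67 |
| 28 | 7 | 0.434 | 0.505 | 2.98 |
| 28 | 21 | 0.081 | 0.646 | 2.55 |

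*Washout.* Five half-lives is 100 to 140 days. Counted from dose 1 it ends on Day 101 to 141. Counted from dose 2 it ends on Day 131 to 171, which is 30 days later.

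**The case against.** The strongest reply is that the case is rare. Section 7.9 says pregnancy is not expected in any participant, and section 4.2 sets a failure rate below 1% for comparable hormonal methods. Suppose that rate is annual and applies to every method, and that all 36 active-arm subjects (3 cohorts of 12) were women of child-bearing potential. Expected conceptions between doses 1 and 2 would then be below 36 × 0.01 × 30/365 = 0.03. The true number would be lower, because not all subjects will be such women, and some conceptions would be too recent to show on Day 31. This stands as an argument about likelihood. It does not remove the gap: the eligibility text in 4.2 and 6.2 decides who enters, and it admits these women.

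A second reply is that sites can test more often. Section 7.9 allows extra tests for local requirements, and section 10 provides for further safety assessments case by case. That is true, so the gap concerns required tests only. Neither provision obliges a site to test before dose 2.

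A third reply is that the kinetic multiple flatters the case. It applies only to active-arm subjects with a pregnancy detectable by Day 31, counts only exposure after that day, and uses single-dose values from healthy subjects across 5 to 240 mg. Over the whole course, two doses instead of one is a factor of 2. These limits are fair. The multiple describes maternal exposure only and says nothing about harm.

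Finally, the Day 41 test has a use: it can catch a conception too recent to show on Day 31 and stop dose 3. That is a reason to consider keeping it.

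**Conclusion.** The concern holds. Under the plan as written, no required pregnancy test can stop dose 2, and dose 3 depends on a result nominally 20 days old. The schedule finding rests on Table 9 alone and needs no assumption.

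The size of the avoidable exposure does rest on assumptions: linear one-compartment kinetics, half-life 20 to 28 days, time to peak 7 to 21 days, and equal doses. On those terms, 39% to 65% of the dose 1 exposure is still to come at Day 31, and giving dose 2 makes later exposure about 2.5 to 3.6 times as large.

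The event is unlikely, and the documents do not say how many women of child-bearing potential will enrol. The matter is participant safety; the primary analysis is unaffected. The sponsor should make the change because it is cheap and makes an existing rule work at every dose.

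**What to change.** In Table 9, add a predose urine pregnancy test at Day 31 and at Day 61. The Day 41 test may be moved to one of these visits or kept. Keeping it would reveal a conception missed at Day 31 about 20 days sooner than waiting for Day 61.

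In section 7.9, require a negative predose result before each dose, and state that this includes any dose resumed or restarted under section 5.6.

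The cost is one extra urine test per woman if Day 41 is moved and two if it is kept. Urine is already scheduled at both dosing visits. The change needs a written amendment with IRB approval under section 10.1, and health authority approval where required. The SAP, sample size and primary analysis stay as they are.
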